5. History of treatment with metformin within the past one year;
6. Treatment with other investigational agents which, at the discretion of the investigator, interfere with safety and/or study outcomes;
7. Current treatment with immunosuppressants (calcineurin inhibitors, corticosteroids, or biological or cytotoxic immunosuppressants, or disease or condition likely to require high dose steroid or

- immunosuppressive therapy);
8. Other conditions or treatments associated with increased risk of infections or treatment with immunosuppressive medications for any reason;
 9. Current treatment with aspirin > 160 mg/day or chronic, daily NSAIDs;
 10. Current (as of time of study screening) or chronic use of antibiotics;
 11. History of keloid formation;
 12. Living with someone who is immunosuppressed and/or at high risk for infectious diseases (for example, HIV+ or taking immunosuppressive medications for any reason), or in a job (e.g. healthcare) in which the subject works with immunosuppressed populations;
 13. Other/confounding neurological or psychiatric condition, unstable medical or psychiatric conditions, contraindications to BCG use and lab abnormalities or concurrent medication use posing risk for BCG or study procedures;
 14. Laboratory abnormalities in B12, Folate, TSH, or other common laboratory parameters that may contribute to cognitive dysfunction per clinician judgment;
 15. Laboratory abnormalities in CBC, electrolytes, LFTs, BUN, Cr, total serum immunoglobulins, ESR, CRP, or urinalysis posing risk to treatment with BCG per clinician judgment;
 16. Laboratory abnormalities in PT-INR, which would pose a risk to performing the lumbar puncture procedure;
 17. Discontinuation of cholinesterase inhibitor or memantine within one month (28 days) prior to baseline visit;
 18. Females who are pregnant, lactating or of child-bearing potential;
 19. If male with female partner(s) of childbearing potential, unwilling or unable to adhere to contraception requirements specified in the protocol.
 20. Increased intracranial pressure as determined on a fundoscopy/neurological examination performed within 30 days of LP;
 21. Administration of live vaccine within 30 days of screening visit or BCG immunizations
 22. Administration of non-live vaccine within 14 days of screening visit or BCG immunizations
 23. If participating in optional MRI: Existing contraindication to MRI per MGH Athinoula A. Martinos Center research guidelines

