6 STUDY PROCEDURES

6.1 Schedule of Events

Activity	Phone Screen	Visit 1 Screen Visit		Visit 2 Baseline Visit	Visit 3	Visit 4	Visit 5	Phone Check 1	Visit 6/ET	Phone Check 2	Phone Check 3
		Day \geq -45		Week 1	Week 4	Week 12	Week 26	Week 39	Week 52	Week 78	Week 104
		SVa	SVb	Day 1	Day 28 + 14	Day 84 \pm 5	Day 182 \pm 14	Day 273 \pm 5	Day 364 \pm 28	Day 546 \pm 28	Day 728 \pm 28
Informed Consent		X									
Inclusion/Exclusion Review	X	X		X							
Demographics	X	X									
Medical History Review	X	X	X	X	X	X	X	X	X	X	X
Concomitant Medication Review	X	X	X	X	X	X	X	X	X	X	X
Family History Review		X									
Vital Signs, Height, and Weight ¹		X	X	X	X	X	X		X		
Physical & Neurological Exam ²		X									
Fundoscopy						X			X		
Screening Labs ³		X									
BCG Vaccination				X	X						
Injection Site Monitoring ⁴					X	X	X		X		
LP Safety Labs ⁵		X				X			X		
Blood Draw for Biomarkers			X	X	X	X	X		X		
CSF Draw for Eligibility & Biomarkers			X			X			X		
Optional MRI ⁶				X					X		
RBANS, NPI-Q, HADS				X		X	X		X		
MoCA, FAQ		X				X	X		X		
CDR				X					X		
DCT Clock				X			X		X		
Adverse Event Review		X	X	X	X	X	X	X	X	X	X

[1] Height measured at screening only. Weight measured at screening, week 26, and week 52

[2] Physical and neurological examinations will be performed at screening and at any other time if indicated per clinician investigator judgement

[3] Eligibility lab tests include CBC w/ diff, CMP, TSH, Folate, B12, HIV antibodies, serum immunoglobulins, ESR, CRP, QuantiFERON-TB Gold Test/T-spot TB test, urinalysis, PT/INR

[4] Vaccination site monitoring may include photographs of the injection site if indicated per clinician investigator judgement

[5] LP safety labs include PT/INR and CBC w/ diff

[6] Multi-sequence MRI for structural and functional measures include T1 MP-RAGE, T2 FLAIR, DWI, DTI, BOLD, ASL

An Open Label Trial to Evaluate the Effects of BCG Immunization on Biomarkers of Inflammation/Immune Response and Alzheimer's Disease in Adults with Mild Cognitive Impairment and Mild-to-Moderate Dementia due to Alzheimer's Disease

Version Date#: October 13, 2022/Version 3.3

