6.2.1.2 Screening Visits (Visit 1; Day ≥-45)

All subjects who are eligible after a telephone pre-screening will be invited to MGH CNY for Screening that will include 2 separate visits.

The first visit (SVa) will take approximately 2 hours and following procedures will be performed:

- Obtain written informed consent from subject
- Review inclusion and exclusion criteria
- Obtain medical and family history including COVID-19 history, concomitant medications and therapies
- Vital signs, height, and weight
- Obtain demographic information
- Neurocognitive and behavioral assessments: MoCA (version 8.1), CDR, FAQ
- Perform a physical, including inspection for BCG scar on either deltoid
- Perform a neurological examination
- Blood draw for screening labs

- CBC with differential
- Comprehensive metabolic panel (CMP)
- Thyroid stimulating hormone (TSH)
- B12
- Folate
- HIV antibodies
- Tuberculosis (QuantiFERON-TB Gold Test/T-Spot TB Test)
- C-Reactive Protein (CRP)
- Erythrocyte sedimentation rate (ESR)
- Serum immunoglobins (IgA, IgG, IgM)
- PT/INR
- Urinalysis
- Assess and document adverse events (AEs) after subject signs ICF

If the participant is still eligible after the first Screening visit (SVa), they will be invited to come back for a second Screening visit (SVb) which will take approximately 1 hour. The following procedures will be performed:

- Vital signs
- Blood draw for biomarkers
- Fasting CSF draw for screening (if required) and baseline biomarkers
- Assess for changes to medical history, concomitant medications and/or adverse events

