6.2.7 Visit 6 (Day 364 ± 28 days)

Subjects will be asked to return to MGH CNY for the final in-person visit at Day 364 (\pm 14 days) to assess study outcomes. This visit will take approximately four hours and will include:

- Vital signs
- Assess any changes to medical history, concomitant medications and/or adverse events
- Neurocognitive and behavioral assessments: FAQ, MoCA (version 8.1), CDR, RBANS (form a), NPI-Q, HADS, DCT Clock
- Blood draw for biomarkers
- Blood draw for LP safety
- Focused Exam: Fundoscopy
- Fasting CSF draw for biomarkers
- MRI (optional)
- Injection site monitoring

6.2.8 Phone Check 2 & 3 (Day 546 ± 28 days, Day 728 ± 28 days)

Subjects will be asked to complete a check-in phone call approximately 18 months and 2 years after the first injection to monitor safety. This will take about fifteen minutes and will:

- Collect any changes to medical history, concomitant medications, and/or adverse events

If the subject reports any new adverse events at the Phone Check that may require follow up, they will be referred to their primary care provider for further evaluation.

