6.2.9 Early Termination Visit

If the subject withdraws from the study before completion of all study visits, they may be invited to return to MGH CNY for a final visit. This visit will take approximately four hours and will include the following measures:

- Vital signs
- Assess any changes to medical history, concomitant medications and/or adverse events
- Neurocognitive and behavioral assessments: FAQ, MoCA (version 8.1), CDR, RBANS (form a), NPI-Q, HADS, DCT Clock
- Blood draw for biomarkers
- Blood draw for LP safety

- Fasting CSF draw for biomarkers
- MRI (optional)
- Injection site monitoring

The option to decline any of the early termination procedures or the entire visit will be given to all participants withdrawing from the study.

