6.3.2 Physical and Neurological Examination

A physical and neurological examination will be performed at the Screening visit. The following systems will be examined: general appearance, head, eyes, ears, nose, throat, neck, chest, heart, abdomen, extremities, edema, peripheral vascular, skin and appendages, musculoskeletal, central nervous system and back. A physical and/or neurological exam may be repeated at any visit if indicated per clinician judgement.

A focused fundoscopy examination will be repeated before the second and third lumbar punctures to assess for increased intracranial pressure.

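### The early-termination visit list in 6.2.9 includes a lumbar puncture but omits the fundoscopy that the Schedule and 6.3.2 attach to it

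*Combined protocol and SAP*

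**What the plan says.** **Early termination.** Section 6.2.9 lists eight items. Among them are "Blood draw for LP safety" and, directly after it, "Fasting CSF draw for biomarkers". Fundoscopy is not listed.

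**Visit 6.** Section 6.2.7 lists the same eight items plus a ninth, "Focused Exam: Fundoscopy", placed between the safety bloods and the puncture.

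**Schedule of Events (6.1).** Visit 6 and early termination share one column. The fundoscopy row is marked at Visit 4 and in that shared column. The row "CSF Draw for Eligibility & Biomarkers" is marked at the second screening visit (SVb), at Visit 4 and in the shared column.

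**Section 6.3.2.** "A focused fundoscopy examination will be repeated before the second and third lumbar punctures to assess for increased intracranial pressure".

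**Screening.** Exclusion 20 reads: "Increased intracranial pressure as determined on a fundoscopy/neurological examination performed within 30 days of LP". The first screening visit (SVa, in 6.2.1.2) includes "Perform a neurological examination"; the puncture comes at SVb: "Fasting CSF draw for screening (if required) and baseline biomarkers". Neither visit list names a fundoscopy.

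**The concern.** A visit list is what staff work from on the day. If the early-termination list is followed as written, the participant has a lumbar puncture without the examination that two other parts of the protocol place before it. The protocol gives the purpose of that examination as a check for raised intracranial pressure, so the omission concerns participant safety and is more than a formatting slip.

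There is also a compliance consequence. The protocol does not say whether the Schedule or the visit narrative prevails. Under 6.2.11, a procedure not attempted for reasons other than illness, injury or disability is a protocol deviation. A visit that complies with 6.2.9 could therefore be a deviation from the Schedule.

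**Working it through.** No statistical quantity bears on this point. The check compares, for each lumbar puncture (LP), the visit list with the Schedule.

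| Time point | LP in visit list | LP in Schedule | Fundoscopy in visit list | Fundoscopy in Schedule |
|---|---|---|---|---|
| Screening (6.2.1.2) | yes, SVb | yes, SVb | not named | not marked |
| Week 12 (6.2.4) | yes | yes | yes | yes |
| Week 52 (6.2.7) | yes | yes | yes | yes |
| Early termination (6.2.9) | yes | yes, shared column | **not named** | **yes, shared column** |

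Early termination is the only row where the visit list and the Schedule disagree.

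**Does 6.3.2 also reach an early-termination puncture?** Section 5.4 offers the visit after the first injection, so it comes after the screening puncture. If the earlier punctures took place as planned, the puncture at early termination is:

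- the second, if withdrawal comes before Week 12;
- the third, if withdrawal falls between Week 12 and Week 52.

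Both are covered by the wording of 6.3.2. A withdrawal during the telephone follow-up after Week 52 would make it the fourth, which that wording does not reach. The Schedule's shared column would still apply.

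**Screening.** Three observations follow from the text.

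1. Section 6.3.2 says the fundoscopy is to be repeated, which implies an earlier one. Neither 6.2.1.2 nor the Schedule names it.
2. The slash in exclusion 20 can mean either examination or both. On the first reading the neurological examination at SVa is enough in content. On the second, something is missing from the lists.
3. The Schedule lets screening start at Day -45, and no maximum interval from SVa to SVb is stated. With SVa at Day -45, the 30-day limit in exclusion 20 is reached at -45 + 30 = Day -15. An SVb on Day -1 would fall 44 days after SVa. The limit can therefore be missed, but nothing in the plan requires or expects so long an interval.

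**The case against.** The strongest defence is that the requirement is not absent from the protocol: the Schedule and 6.3.2 both carry it, and one list fails to repeat it. Participants may also decline any early-termination procedure. The first part is true and limits the finding to an inconsistency, but with no stated order of precedence it does not settle which text staff should follow. The second does not help a participant who accepts the puncture. The 6.2.9 list also appears to break across a page at exactly the place where the line would sit, so the source page deserves a look. Nothing there indicates lost text.

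A reader might infer more than the documents support, in three ways.

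- **That screening contradicts the Schedule.** It does not: both omit fundoscopy there. The screening examination in 6.3.2 covers the eyes and central nervous system and may already include it.
- **That the 30-day and 45-day limits clash.** They govern different intervals, examination to puncture and screening to baseline. Both can be met, and 6.3.2 allows the examination to be repeated at any visit if indicated.
- **That the number affected can be stated.** Taking the 12 expected completers (4.2) from the approximately 15 subjects in 8.1 gives 3, but neither section gives a count of withdrawals, and the visit is by invitation. Counting up to 25 screening punctures also fails. Anyone who signs consent is counted as enrolled (6.2.1.3), only those still eligible after SVa reach SVb, and roll-over participants join at Visit 3 of the earlier trial (6.1.1).

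**Conclusion.** The early-termination point holds. Section 6.2.9 contradicts the Schedule's shared Visit 6 and early-termination column, and it does not match 6.3.2 for a second or third puncture. The conclusion rests on reading the Schedule's marks by column position and on the 6.2.9 list being complete as printed. How many participants are affected cannot be worked out from the documents; it could be none. The trial's endpoints and analyses are untouched. The point is worth correcting because the omitted item is a safety check in a list that staff would use directly.

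For screening, the supportable conclusion is narrower: an implied first fundoscopy that no list names, an exclusion criterion with two readings, and a 30-day limit with no stated SVa-to-SVb interval to protect it. These need clarification. They are not an error that the documents establish.

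**What to change.** Reconcile 6.2.9 with the shared Visit 6 and early-termination column of the Schedule and with 6.3.2, so that all three say the same about the examination before an early-termination puncture. If the investigators keep the visit list and the Schedule as parallel sources, a sentence stating which prevails would prevent similar conflicts.

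As a secondary step, the investigators should reconcile exclusion 20, the Schedule's fundoscopy row, 6.2.1.2 and 6.3.2. The text should make clear what examination exclusion 20 refers to at screening, where it is recorded, and how its 30-day limit is kept when SVa and SVb are separate visits. The clinical rule is theirs to decide; this point asks only that the passages agree.

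The cost is a few lines in the next amendment and the matching visit checklist. Reconciling 6.2.9 with the Schedule as it stands would add no procedure that the Schedule does not already carry.

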6.2.10 Protocol Deviations

A protocol deviation is any noncompliance with the current clinical trial protocol. The noncompliance may be on the part of the subject, the PI or Co-Is, or the study staff. As a result of deviations, corrective actions will be developed by the PI and implemented promptly. All deviations from the protocol must be addressed in the subject's documents. Protocol deviations will be sent to the IRB per their guidelines and entered in the Protocol Deviations Log.

6.2.11 Missed Visits and Procedures

Missed visits and any procedures not performed (not attempted) for reasons other than illness, injury, or progressive disability (i.e.: a subject is physically unable to perform them) will be reported as protocol deviations.

Procedures or visits not performed due to illness, injury, or disability, including procedures that were attempted but failed (i.e.: blood samples unable to be drawn after multiple attempts or weight unable to be obtained due to subject immobility) will not be reported as protocol deviations.

6.3 Clinical Assessments

Assessments will be performed at designated time-points throughout the study for clinical evaluation. In addition to the assessments evaluated below, subjects will provide information on their demographics, past medical and AD history, family history, medication usage, and vaccination history.

6.3.1 Safety Measures

6.3.1.1 Vital Signs, Height, Weight

Vital signs, including systolic and diastolic blood pressure, pulse rate (radial artery)/minute, respiratory rate/minute, and temperature will be assessed at all in-person visits. Height will be measured at the screening visit only. Weight will be measured at screening, week 26, and week 52 visits. Verbal weight may be documented for those subjects utilizing a wheelchair.

6.3.1.2 Clinical Laboratory Assessments

Study participants will be asked to provide the volumes of blood and urine detailed in Table 1 for eligibility (at screening) and safety lab analyses. The participant will have their whole blood collected by either a nurse or phlebotomist from a peripheral vein (or finger prick for point of care coagulation test). Blood will be handled, processed, and analyzed in accordance with regulations set forth by the American Society for Clinical Pathology and the College of American Pathologists.

Table 1. Safety Laboratory Tests

Visit	Labs	Volume required
Screening (SV1a)	PT/INR, Complete Blood Count w/ differential, Complete Metabolic Panel, C-Reactive Protein, Erythrocyte Sedimentation Rate, HIV Antibody, QuantiFERON-TB Gold test/T-spot TB test, Folate, B12, Serum immunoglobins (IgG, IgA, IgM), TSH, Urinalysis	33 mL blood, 10 mL urine
Screening (SV1b)	N/A	N/A
Week 1	N/A	N/A
Week 4	N/A	N/A
Week 12	Complete Blood Count w/ differential and PT/INR	6 mL
Week 26	N/A	N/A
Week 52	Complete Blood Count w/ differential and PT/INR	6 mL

All subjects will have safety laboratory tests at the designated visits outlined in the protocol. These samples will be analyzed at MGH Core Laboratory. The SI may order additional testing, if thought to be necessary, to further assess an adverse event (AE), or if there is any suspicion that a subject may be pregnant, throughout the course of the study.

Tests for Complete Blood Count (CBC), Comprehensive Metabolic Panel (CMP), and International Normalized Ratio (INR) may be performed with CLIA-waived point of care devices: Sysmex XW-100 CBC Analyzer, Piccolo Xpress Chemistry Analyzer, and the Roche CoaguChek XS Plus PT/INR Analyzer, respectively.

6.3.2 Physical and Neurological Examination

A physical and neurological examination will be performed at the Screening visit. The following systems will be examined: general appearance, head, eyes, ears, nose, throat, neck, chest, heart, abdomen, extremities, edema, peripheral vascular, skin and appendages, musculoskeletal, central nervous system and back. A physical and/or neurological exam may be repeated at any visit if indicated per clinician judgement.

A focused fundoscopy examination will be repeated before the second and third lumbar punctures to assess for increased intracranial pressure.

6.3.3 Phlebotomy for Research: Target Engagement, Cytokine Levels and Biomarker Analysis

Subjects will provide additional blood samples for biomarker analysis at all in person visits. Target engagement will determine whether the subject's immune system has responded to BCG. In general, whole blood will be either collected and utilized for biochemical / metabolic assays, or spun in EDTA-containing tubes with plasma being frozen for cytokine analysis of IIR and / or AD biomarkers. Remaining plasma may be used for other biochemical analyses. Peripheral blood mononuclear cells (PBMCs) will be isolated from the cell pellets, some of which will be frozen for later culturing and cell-stimulation studies. Other PBMCs will be further isolated into subpopulations of cells and frozen for epigenetic analyses (e.g. ATACseq) and possibly subject to other immunostaining or quantitative biochemical assays.

In addition to these analyses, blood will also be collected for routine blood tests that will be used for research purposes including Complete Blood Count with differential (CBC w/ diff), C-Reactive Protein (CRP), and Erythrocyte Sedimentation Rate (ESR). CRP and ESR tests will be performed at a central laboratory. CBC w/ diff may be performed either on-site using a CLIA-waived point-of-care device (Sysmex XW-100 CBC Analyzer) or at a central laboratory. Blood volumes collected at each visit are detailed in Table 2.

Table 2. Blood Collection for Research

Visit	Blood volume required for biomarker analyses (mL)	Volume required for routine tests(mL)	TOTAL (mL)
Screening (SV1a)	0	0	0
Screening (SV1b)	75	0	75
Week 1	50	0	50
Week 4	75	3 for CBC w/ diff	78
Week 12	125	9 for CBC w/ diff, ESR, CRP	134
Week 26	125	9 for CBC w/ diff, ESR, CRP	134
Week 52	125	6 for ESR, CRP	131
Total	575	27	602

Blood processing will occur on site at MGH. Blood samples will be de-identified, codified, and stored on-site. Blood samples will be stored for research until they are used, damaged, or otherwise unfit for analysis. Some biomarker analyses may be done at Harvard-affiliated core labs.

Samples drawn for biomarker research may also be used for genome analyses in the future. Subjects will not receive the results of these studies if they are done and genetic research results will not be placed in the subjects' medical records.

6.3.3.1 Sending Blood Samples to Research Collaborators Outside Mass General Brigham

Blood samples may be sent to Merck & Co. and Active Motif, Inc. for analyses. Samples may include isolated PBMCs or their derivatives. Samples will be de-identified with a study code and visit date.

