3 STUDY DESIGN

3.1 Overall Study Design and Plan

This single-site, open-label trial will investigate the effects of BCG vaccination on IIR and AD biofluid biomarkers, magnetic resonance imaging (MRI) biomarkers, and neurocognitive/behavioral functioning over a one-year period in older adults with mild cognitive impairment (MCI) to mild-to-moderate dementia due to AD. This study will also gather data on tolerability and safety. Safety will continue to be followed in the second year by phone.

Up to twenty five participants meeting eligibility criteria will be enrolled. Each participant will receive two intradermal BCG vaccinations spaced 4-6 weeks apart and will be evaluated 12, 26, and 52 weeks after the initial immunization. Cerebrospinal fluid (CSF), blood, MRI (in a subset of patients), and neurocognitive/behavioral assessments will be collected at Screening (CSF, blood, and cognitive/behavioral), Week 1 (MRI and cognitive/behavioral), Week 4 (blood), Week 12 (CSF, blood, and cognitive/behavioral), Week 26 (Blood and cognitive/behavioral) and Week 52 (all) to assess biomarkers and safety. Safety measures, including updated medical history and adverse events, will be collected at Week 78 and Week 104.

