3.3.2 CSF and Blood Biomarker Outcomes

CSF and blood will be collected at Screening, Week 4 (blood only), Week 12, Week 26 (blood only), and Week 52 visits to examine biochemical biomarkers of:

1. Target engagement: BCG, purified protein derivative (PPD) and / or mycobacterium tuberculosis (heat-killed, mTB) – induced cytokine response in peripheral blood cells will be used to evaluate for BCG vaccine-induced immunity.
2. Pharmacodynamic response: a) Circulating cytokines and other related blood- and CSF-based IIR biomarkers relating to innate and adaptive immune responses; b) Epigenetic changes in peripheral blood cells and / or CSF- derived cell populations as indicators that BCG can lead to long term changes in peripheral and central nervous system immune cells.
3. AD pathophysiology: Amyloid- β 42/40, phospho-tau, total tau and / or neurofilament light protein biomarkers (ATN) and other exploratory AD-relevant synaptic and IIR biomarkers may be compared within subjects over time and between subjects and groups.
4. BCG effects on the interactions of IIR and amyloid: We will perform PBMC stimulation with A β 42 and positive-control antigens (e.g. lipopolysaccharide) and measure the molecular response in the supernatant at multiple timepoints after BCG /treatment. A β 42 has immunostimulatory / inflammatory effects that increase with AD progression and may be modulated by an immune-provoking stimulus such as BCG.
5. Additional related Alzheimer's Disease and immune measures in plasma, CSF, and their cell populations at the transcriptional, protein, or epigenetic levels.

We have several robust platforms in the [name] lab (which serves as the Biomarker Core of the Massachusetts Alzheimer's Disease Research Center) to conduct these assays, including highly validated Euroimmun assays, Fujirebio Lumipulse assays, Meso Scale Discovery with plates run on a new Tecan EV0200 multi-functional robotic liquid handling platform, and Quanterix SR-X for ultrasensitive Simoa assays. We have exhaustively validated many assays specifically for use in short-term clinical trials⁴⁹, and all assays that we propose demonstrate good precision and biotemporal stability. Change in a composite score from Baseline will be used as an outcome of response to BCG.

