6.3.4.1 Sending CSF Samples to Research Collaborators Outside Mass General Brigham

CSF cell samples may be sent to Merck & Co. and Active Motif, Inc. for analyses. Samples will be de-identified with a study code and visit date.

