8.3 Biofluid Biomarker, Clinical and Neuroimaging Endpoints

The change in the following assessments from Screening and/or Baseline to each post-baseline visit as described below based on the Schedule of Activities after BCG vaccination:

- Biochemical Biomarkers in Blood (Screening/Baseline, Weeks 4, 12, 26, 52) and CSF (Screening/Baseline, Weeks 12, 52) : a) Target engagement (e.g., PPD-induced PBMC cytokine release); b) Pharmacodynamic response (e.g., circulating cytokines in blood and CSF); c) AD pathophysiology (e.g., amyloid-b, tau and neurofilament light in CSF and blood); d) PBMC stimulation with AD-relevant immunogens (e.g., amyloid-b); e) Other novel biochemical biomarkers
- Clinical Neurocognitive and Behavioral Measures (Baseline, Week 12, 26 and 52): MoCA, RBANS, CDR-SB, NPI-Q, HADS, DCT Clock and FAQ
- Multi-Sequence Structural and Functional MRI (Baseline, Week 52)

Mixed-effects Model for Repeated Measures models will be used for biofluid and clinical endpoints to calculate differences at each post-baseline visit in which the biomarker is collected using baseline assessment as a covariate. Observed Case analysis will be used for differences in change of MRI measures over 52 weeks.

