9.8 Genetic Research Risks

The study includes the potential to generate genetic data from patient samples. Genetic information that results from this study does not have medical or treatment importance at this time. Genetic information obtained in this study will not be placed in the medical record. Taking part in a genetic study may also have a negative impact on family or other relationships. We will inform subjects that there may be new technologies that may be developed in the future that may allow the linking of genetic or medical information back to subjects.

To maximize confidentiality, all samples and the information associated with the samples will be coded to prevent the exposure of the participant's information and identity. In addition, sample information is stored in one secured database while genetic data is stored in an independent secured database.

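### Samples that may go to two outside companies carry the visit date, which can show assay staff which are pre- and post-BCG, and nothing in the plan masks time point

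*Combined protocol and SAP*

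**What the plan says.** Section 6.3.3.1 permits shipment of blood: "Blood samples may be sent to Merck & Co. and Active Motif, Inc. for analyses". It adds that this may include isolated PBMCs or material derived from them. Section 6.3.4.1 uses the same form for CSF: "CSF cell samples may be sent to Merck & Co. and Active Motif, Inc. for analyses". Both sections give the same labelling rule: "Samples will be de-identified with a study code and visit date".

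On design, Section 3.1 states: "This single-site, open-label trial will investigate the effects of BCG vaccination on IIR and AD biofluid biomarkers". It continues: "Each participant will receive two intradermal BCG vaccinations spaced 4-6 weeks apart". Section 8.3 defines the biomarker endpoint as "The change in the following assessments from Screening and/or Baseline to each post-baseline visit", and Section 3.2 lists biomarker change among the primary objectives. Section 3.3.2 says AD markers "may be compared within subjects over time and between subjects and groups", but the plan defines no comparison group.

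No section masks assay staff to visit, randomises run order, or requires assay quality decisions to be settled before results are joined to visits. The protocol does not say whether the study code is per participant or per sample.

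**The concern.** With no control arm, the biomarker evidence is the difference between earlier and later samples from the same person. A laboratory that can put one person's tubes in date order can, with the schedule, tell which are pre- and post-vaccination.

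Section 6.3.3 foresees cell stimulation, epigenetic work such as ATAC-seq, and immunostaining on blood cells. Assays of this kind usually involve choices about which samples or runs to exclude and which to repeat. The protocol does not describe those choices. If they are made with time point visible, they can lean, without intent, towards or away from a post-BCG change, and there is no concurrent arm in which the same leaning would cancel. The study is small: about 15 subjects (Section 8.1), with 12 expected to complete (Section 4.2).

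**Working it through.** The plan gives no figure to reproduce here. The question is whether dates under one participant code separate pre-BCG from post-BCG samples. The protocol's visit windows answer it.

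**Inputs, in days from first injection**
- Screening: up to 45 days before (Section 6.2.2), taken as −45 to −1.
- Day 1 draw: up to 3 days early (Section 6.2.2), so −3 to 0. It is taken as before the injection, following the order of the list in that section.
- Week 4: 28 to 42 (Section 6.2.3).
- Week 12: 79 to 89 (Section 6.2.4).
- Week 52: 336 to 392 from the heading of Section 6.2.7 and the schedule. The sentence under that heading gives ± 14, so 350 to 378. Both were run.
- Rollovers first given placebo: their Day 28 visit becomes Day 1 (Section 6.1.1). Their screening therefore lies 28 to 42 days further back, at −87 to −29.

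**Formula.** Shortest gap = earliest later visit − latest earlier visit. Longest gap = latest later visit − earliest earlier visit.

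**CSF (Screening, Week 12, Week 52)**

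| Pair | Gap, days | Rollover first given placebo |
|---|---|---|
| Screening to Week 12 | 79 − (−1) = 80 to 89 − (−45) = 134 | 79 + 29 = 108 to 89 + 87 = 176 |
| Week 12 to Week 52 | 336 − 89 = 247 to 392 − 79 = 313 | same |
| Screening to Week 52 | 336 + 1 = 337 to 392 + 45 = 437 | 336 + 29 = 365 to 392 + 87 = 479 |

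The highest Screening-to-Week-12 gap (176) is below 247, and the highest Week-12-to-Week-52 gap (313) is below 337. The three kinds of pair never overlap. With the ± 14 window the last two rows narrow to 261–299 and 351–423 (379–465 for those rollovers), and the result is the same. So even two CSF samples from one person can be classified, and in a full set of three the first is pre-dose.

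**Blood (SVb, Day 1, Weeks 4, 12, 26, 52)**
- Complete set of six: the first two are pre-dose and the other four post-dose.
- Lone pair: SVb to Day 1 is up to 45 days. Day 1 to Week 4 is 28 − 0 = 28 to 42 + 3 = 45. Week 4 to Week 12 is 79 − 42 = 37 to 89 − 28 = 61. A 40-day gap could therefore be two pre-dose samples, one of each, or two post-dose samples.

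**Limits.** The windows assume scheduled visits with no repeat screening. An early-termination draw or a re-screen would add dates outside them. If codes were unique to each tube and participants entered at different calendar times, a date alone would not reveal time point.

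**The case against.** The strongest reply is that this is an openly open-label, exploratory study sized on feasibility, that it promises no laboratory blinding, and that nothing is contradicted. That is correct: this is an unaddressed risk of bias. But treatment being open to participants and clinicians does not require assays to be read with time point visible, and masking the laboratory conflicts with nothing in the plan.

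Other parts of the reply stand. Shipment is permitted, not certain. Neither section says which assays the companies would run. Section 3.3.2 describes PBMC stimulation as the study team's own work and associates the biomarker assays with in-house platforms. Of the CSF, only cells are listed for shipment. Much of the biomarker objective is therefore not shown to be touched by this label. Blood is processed on site (Section 6.3.3), so staff handling fresh samples may know the visit whatever the tube says.

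A reader might infer three stronger things, none of which the documents support.

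- *That a dated label breaks the protocol's own promise of de-identification.* Section 9.8 says "all samples and the information associated with the samples will be coded to prevent the exposure of the participant's information and identity", and a study code meets that. Section 12.1 cites a regulatory definition for exported datasets only, and its text is not in the documents. No standard is set for shipped samples that a date would breach.
- *That laboratory masking is the only blinding left.* MRI analysis (Section 6.3.6) could also be masked to scan order.
- *That one exclusion could move the result by nearly one standard error.* With an assumed within-person correlation of 0.8, the SE of mean change is √(2 × 0.2)/√n = 0.163 SD at n = 15 and 0.183 SD at n = 12. A post-dose value 2 SD from the rest shifts the visit mean by 2/15 = 0.13 to 2/12 = 0.17 SD, or 0.82–0.91 SE. That sets a cross-sectional shift against a paired SE. Under the same correlation the person's baseline is expected to be 1.6 SD high, so the change is off by 0.4 SD. Dropping the person then moves mean change by 0.4/15 to 0.4/12 = 0.027–0.033 SD, about 0.16–0.18 SE. The documents give neither a correlation nor an SD, so no figure of this kind can be relied on.

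**Conclusion.** The point holds as a specific bias risk that is cheap to remove. For samples actually sent out under a participant-level code, the label shows the pre/post order: fully for CSF (one pre-dose, two post-dose) and for a complete blood series (two pre-dose, four post-dose). Nothing in the plan prevents exclusion and re-run decisions from being made with that knowledge, and the contrast revealed is the one on which a primary objective rests.

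The conclusion rests on three assumptions: that samples are shipped, that the code is per participant, and that the laboratory knows the visit schedule. Pairing a code with a date reads most naturally as a participant code, but that is inference. If the code is per sample, one sentence saying so would largely answer the point. The size of any bias is unknown.

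**What to change.** In Sections 6.3.3.1 and 6.3.4.1, state that the code is per participant and replace the date on the label with a random sample number that shows neither visit nor date. Keep the linking key with the study team. Join results to visits only after assay quality decisions, including exclusions and re-runs, are final. Keeping the participant code lets the laboratory still run one person's samples together.

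Use the same label for stored samples batch-assayed in the in-house and Harvard-affiliated laboratories where practicable. It need not extend to fresh blood processed on the day of the visit.

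The cost is maintaining one linking list and, where the laboratory needs storage time, supplying it in a form that does not reveal the visit. No extra visits or samples are needed. The change should be made before any shipment, because time point cannot be masked again once dated samples have been assayed.
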